At the Clinically Symptomatic Respiratory Illness Unscheduled Visit, Study Investigators will evaluate the subject and perform a targeted physical exam based on the symptoms reported by the subject and including vital signs and temperature. Any medications used to treat the clinically symptomatic respiratory illness, including antibiotics and any change to current medications, will be recorded. In addition, a nasopharyngeal swab will be obtained. Subjects who have a productive cough that is changed from baseline should have a sputum specimen obtained for gram stain and culture. If clinically indicated, blood and urine samples needed to clinically evaluate the subject may be obtained at this visit. Subjects who have influenza-like illness signs and symptoms (such as 1 or more respiratory symptom (cough, sore throat or nasal symptoms) and 1 or more constitutional symptom (such as body aches or feverishness/chills) should have a rapid influenza diagnostic test (RIDT) done. Subjects with influenza-like illness who have influenza detected by RIDT or nasopharyngeal swab PCR should receive anti-influenza treatment per local standard of care, unless contraindicated, and/or other appropriate medical care. If subjects are unable or unwilling to return to the study site for the Clinically Symptomatic Respiratory Illness Unscheduled Visit, the nasopharyngeal swab and, if indicated, a sputum specimen and RIDT should be obtained at a home visit by trained personnel. Appropriate medical care (including referral to their healthcare provider or to a hospital, if indicated) should be provided for all clinically symptomatic respiratory illness episodes (including anti-influenza treatment, if indicated, in subjects diagnosed with influenza) per local standard of care. Study drug treatment can be continued in subjects who require antibiotics or anti-influenza medication for treatment of an RTI.

Weeks 2-12 Visits

Provided the study drug continues to be well tolerated, subjects will be treated with study drug for 16 weeks, during which time they will return to the clinic every 2 weeks (visits Week 2, 4, 6,

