5.4.5. Prohibited Medications

Use of the treatments displayed in Table 5-2 is NOT allowed while subjects are taking study drug. Strong inhibitors and inducers of CYP3A4 and CYP1A2 are prohibited because they may substantially alter RTB101 blood levels. Immunosuppressive agents are prohibited because they may inhibit the immune response to infections and confound efficacy evaluations. Digoxin is prohibited because it is a narrow therapeutic index substrate of P-gp, and RTB101 may inhibit P-gp in the gut. Use of any prohibited concomitant medications including St. John's wort while on study drug should be documented as a protocol deviation.

Table 5-2 Prohibited Concomitant Medications

Medication	Prohibition Period	Action to be taken
Strong inhibitors of CYP3A4 (e.g., ketoconazole, itraconazole, clarithromycin, telithromycin, voriconazole, ritonavir).	While on study drug	Discontinue study treatment while taking prohibited medication and for 5 half-lives after discontinuation of the prohibited medication and document as a protocol deviation
Strong inducers of CYP3A4 (e.g., carbamazepine, phenytoin, rifampicin, rifabutin, St. John's wort).	While on study drug	Discontinue study treatment while taking prohibited medication and for 5 half-lives after discontinuation of the prohibited medication and document as a protocol deviation
Strong inhibitors of CYP1A2 (e.g., ciprofloxacin, enoxacin, fluvoxamine(a), zafirlukast).	While on study drug	Discontinue study treatment while taking prohibited medication and for 5 half-lives after discontinuation of the prohibited medication and document as a protocol deviation
Strong inducers of CYP1A2 (e.g., rifampicin).	While on study drug	Discontinue study treatment while taking prohibited medication and for 5 half-lives after discontinuation of the prohibited medication and document as a protocol deviation
Immunosuppressive therapy including prednisone > 10 mg daily except for acute treatment of conditions such as exacerbation of asthma	While on study drug	Discontinue study treatment while taking prohibited medication and for 5 half-lives after discontinuation of the prohibited medication and document as a protocol deviation
Digoxin	While on study drug	Discontinue study treatment while taking prohibited

		medication and for 5 half-lives after discontinuation of the prohibited medication and document as a protocol deviation
--	--	---

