6.3. Dietary, Fluid and Other Restrictions

During Screening/informed consent review, Baseline visit and subsequent study visits, the subjects will be informed and reminded of the following restrictions:

- No grapefruit or Seville oranges or their juices, should be consumed for 14 days prior to dosing until 7 days following the last dose. Any consumption of grapefruit or Seville orange or their juices during this period should be documented as a protocol deviation.
- Subjects must be instructed to take the daily dose of study drug with breakfast and should try to eat similar types of food at breakfast while taking study drug. Subjects who are participating in the PK assessments will be given their study drug together with a light meal provided at the site at the Week 4 Visit and at the Week 12 Visit. If PK sampling cannot be performed at the Week 4 visit for logistical reasons, it should be collected at the Week 6 visit instead, with the same timing of dose relative to a light meal provided at site.

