6.7.2. Laboratory-Confirmed Clinically Symptomatic Respiratory Illness

When a subject reports symptoms of a respiratory illness in which at least one unique respiratory symptom (runny nose, sneezing, stuffy nose, sore throat, hoarseness, or cough) is reported on 2 consecutive entries in their eDiary, the sites will contact the subject and instruct the subject to come to the study site if they are able to within 48 hours for evaluation and to obtain a nasopharyngeal swab. Subjects should only have one nasopharyngeal swab obtained during each episode of a respiratory illness. Please refer to the SOM for more details. Laboratory confirmation of clinically symptomatic respiratory illness will be obtained using three methods:

- The FILMARRAY Respiratory panel polymerase chain reaction (PCR) Assay of nasopharyngeal swabs in all subjects
- Sputum gram stain and culture obtained in subjects with a productive cough that is new or a change from their normal baseline
- RIDT obtained in subjects with influenza-like illness symptoms (such as 1 or more respiratory symptom (cough, sore throat or nasal symptoms) and 1 or more constitutional symptom (such as body aches or feverishness/chills)).

Subjects who are unwilling or unable to come to the study site for an unscheduled visit should have the nasopharyngeal swab (and sputum specimen or RIDT , if indicated) obtained at a home visit by trained personnel. All subjects with influenza-like illness who have influenza detected by RIDT or nasopharyngeal swab PCR should receive anti-influenza treatment per local standard of care, unless contraindicated, and/or other appropriate medical care.

Study drug treatment can be continued in subjects who require antibiotics or anti-influenza treatment for treatment of an RTI.

Laboratory-confirmed clinically symptomatic respiratory illness will be defined programmatically as a symptomatic respiratory illness that meets the prespecified clinical diagnostic criteria outlined in [Section 6.7.1](#) and is associated with a laboratory-confirmed pathogen detected by one or more of the 3 methods described above. Further details will be provided in the SAP.

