Moderate inhibitors (use with caution)

Amprenavir, aprepitant, atazanavir, cimetidine, ciprofloxacin, crizotinib, darunavir, diltiazem, elvitegravir, erythromycin, fluconazole, fosamprenavir, grapefruit juice, imatinib, *Schisandra sphenanthera*, tipranavir, tofisopam, verapamil

Table 13-2 Strong CYP4503A4 Inducers (prohibited)

Avasimibe, carbamazepine, phenobarbital, phenytoin, rifabutin, rifampin, St. John's wort, troglitazone

Moderate Inducers (use with caution)

Bosentan, efavirenz, etravirine, modafinil, nafcillin, ritonavir, talviraline, tipranavir, pioglitazone

Table 13-3 Strong CYP4501A2 Inhibitors (prohibited)

Ciprofloxacin, enoxacin, fluvoxamine(a), zafirlukast

Table 13-4 Strong CYP4501A2 Inducers (prohibited)

Rifampin

Table 13-5 Narrow Therapeutic Index P-gp Substrates (prohibited, example below)

Digoxin

13.2. **Appendix 2: Algorithm for Management of Pneumonitis**

To be applied only if:

1. radiological findings of newly-occurring/worsening lung infiltration
2. absence of infectious or malignant etiology (based on diagnostic procedure such as bronchoscopy &/or trial of anti-infectious treatment, as appropriate)

CTC Grade	Investigations	Additional Measures
1	CT scan w/ lung windows PFTs	Discontinue study drug
2 and 3	Lung monitoring CT scan (if only chest X-ray carried out) Involve pulmonologist (consider bronchoscopy) PFTs	Discontinue study drug bronchoscopy if indicated (to exclude infection or malignancy) short course of steroids to be considered if symptoms important or persisting beyond 1 month lung monitoring for 2 months then return to initial monitoring frequency if no recurrence. ----- continue monthly lung monitoring until return to grade \leq 1 or stabilization
4	Lung monitoring CT scan (if only chest X-ray carried out) Involve pulmonologist (consider bronchoscopy) Repeat PFTs, if possible	Discontinue study drug bronchoscopy with BAL, if possible steroids and other support as necessary continue monthly lung monitoring until return to grade \leq 1 or stabilization

Notes:

PFT (Pulmonary function tests) to include: diffusing capacity corrected for hemoglobin (DLCO); spirometry; resting oxygen saturation.

Guideline for significant deterioration in lung function from baseline: Decrease in Spirometry and/or DLCO of 30% and/or O₂ saturation \leq 88% at rest on room air.

Duration and dose of course of corticosteroids will vary according to circumstances but should be as limited as possible. Consider tapering dosage at end.

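### Sections 3.1 and 6.7.2 let study drug continue with any antibiotic for an RTI, while Table 5-2 requires a stop for six named antibiotics; Appendix 1 also gives ciprofloxacin, ritonavir and grapefruit juice conflicting statuses

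*Protocol*

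**What the plan says.** Two passages give a general permission. Protocol Section 3.1, under the unscheduled illness visits, states: "Study drug treatment can be continued in subjects who require antibiotics or anti-influenza medication for treatment of an RTI". Section 6.7.2, on laboratory confirmation, states: "Study drug treatment can be continued in subjects who require antibiotics or anti-influenza treatment for treatment of an RTI". Neither carries an exception or points to the prohibited list.

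Section 5.4.5 says the opposite for named agents: "Use of the treatments displayed in Table 5-2 is NOT allowed while subjects are taking study drug". Table 5-2 then lists "Strong inhibitors of CYP3A4 (e.g., ketoconazole, itraconazole, clarithromycin, telithromycin, voriconazole, ritonavir" and "Strong inhibitors of CYP1A2 (e.g., ciprofloxacin, enoxacin, fluvoxamine(a), zafirlukast", and its inducer rows add rifampicin and rifabutin. The action in each row is to stop study drug while the agent is taken and for 5 half-lives afterwards, and to record a protocol deviation.

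Appendix 1 (Section 13.1) repeats the classes with more names. Its caution list of moderate CYP3A4 inhibitors begins "Amprenavir, aprepitant, atazanavir, cimetidine, ciprofloxacin" and later includes grapefruit juice. Its prohibited list of strong CYP1A2 inhibitors reads "Ciprofloxacin, enoxacin, fluvoxamine(a), zafirlukast". Ritonavir is among the prohibited strong CYP3A4 inhibitors and also among the moderate inducers to be used with caution. On diet, Section 6.3 says: "No grapefruit or Seville oranges or their juices, should be consumed for 14 days prior to dosing". That bar runs until 7 days after the last dose, and any consumption in the period counts as a deviation.

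**The concern.** A site treating a respiratory infection with, say, clarithromycin can find one sentence that lets study drug continue and a table that requires it to stop. The route through the protocol favours the first: the Section 6 entry for unscheduled illness visits only refers back to Section 3.1, which holds the unqualified permission. That section also calls for care to local standard, including referral to outside providers.

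The protocol treats the interaction as a matter of substance, since Section 5.4.5 bars these inhibitors and inducers because of their possible effect on RTB101 blood levels. If sites follow different passages, subjects on the same antibiotic will have different exposure, and the same event will be a recorded deviation at one site and not at another. Missed doses and major deviations also decide membership of the per-protocol set (Protocol 9.1, SAP 5.4).

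**Working it through.** The point rests on text, so the check sets the instructions side by side.

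| Agent | Sections 3.1 and 6.7.2 | Table 5-2 | Appendix 1 |
|---|---|---|---|
| Clarithromycin | may continue | stop, deviation | prohibited (13-1) |
| Telithromycin | may continue | stop, deviation | prohibited (13-1) |
| Enoxacin | may continue | stop, deviation | prohibited (13-3) |
| Rifampicin (rifampin in Appendix 1) | may continue | stop, deviation | prohibited (13-2, 13-4) |
| Rifabutin | may continue | stop, deviation | prohibited (13-2) |
| Ciprofloxacin | may continue | stop, deviation | prohibited (13-3) and caution (moderate CYP3A4 inhibitor) |
| Ritonavir | not an antibiotic | stop, deviation | prohibited (13-1) and caution (moderate inducer) |
| Grapefruit juice | not applicable; barred in 6.3 | not listed | caution (moderate CYP3A4 inhibitor) |

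1. **Permission against Table 5-2.** The first six rows conflict. The permission covers antibiotics for an RTI as a class, and Table 5-2 takes six members out of it, but neither passage mentions the other.
2. **Within Appendix 1.** Intersecting all its prohibited lists with both its caution lists gives exactly two agents, ciprofloxacin and ritonavir. Only ciprofloxacin is an antibiotic; the other five antibiotics in the table are consistently prohibited.
3. **Appendix 1 against Section 6.3.** Grapefruit juice is allowed with caution in one place and barred in the other.
4. **Reach into the per-protocol set.** That set requires fewer than 20% of doses missed. Assuming one dose a day for 16 weeks, 16 × 7 = 112 doses and 0.20 × 112 = 22.4. So 22 missed doses (22/112 = 19.6%) keep a subject in and 23 (23/112 = 20.5%) take the subject out. With the 111 days that SAP 9.3.2.1 uses for 16 weeks, the limit is 22.2 and the cut is again 23. The documents give no antibiotic course lengths or half-lives, so whether a Table 5-2 stop would reach 23 days cannot be determined.

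**The case against.** The best defence is that the passages can be read together. The permission is only permissive: needing an antibiotic is not in itself a reason to stop, which agrees with Section 5.5.2, where RTI treatment is not among the reasons for permanent discontinuation. Table 5-2 is then the specific rule for named agents, and it asks for a time-limited stop. Section 5.4.4 supports this reading: every concomitant medication is to be checked against the prohibited list, and the Medical Monitor contacted in case of doubt whenever a new medication is needed. The double listings have an explanation too. Ciprofloxacin is classed by two enzymes and ritonavir as both inhibitor and inducer, and Table 5-2 gives each a single status.

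Much of this stands. It rules out saying that the protocol offers sites no help, or that the antibiotics in general are listed both ways. It does not remove the problem. The joint reading is reasonable but unwritten: Sections 3.1 and 6.7.2 refer to neither 5.4.4 nor 5.4.5, and a site holding an explicit permission may see no doubt to raise. Nor does 5.4.4 settle Appendix 1, because a site that checks ciprofloxacin there finds both answers.

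A reader might also infer that the conflict falls on all subjects who have the endpoint. At the planning rates those would number 533 × 0.282 = 150 on placebo and 533 × 0.197 = 105 on RTB101, 255 in all. The documents do not support that. A CSRI is defined by programme from eDiary symptoms and includes common colds, and an RTI treated with an antibiotic need not meet the definition. The 255 is the projected CSRI count, with no antibiotic-use rate or listed-agent share applied, and the documents give neither.

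**Conclusion.** The inconsistency is real and should be corrected. For six named antibiotics the protocol both permits continuing study drug and requires stopping it for a time. Appendix 1 gives ciprofloxacin and ritonavir two statuses each, and grapefruit juice one that disagrees with Section 6.3.

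Its size cannot be stated as a number, because it reaches only subjects given a listed agent. What is exposed is subject safety, consistency of exposure between sites, deviation counts and the per-protocol analysis, which is supplemental (Protocol 9.4.4.1, SAP 9.3.2.2) and whose membership is decided at a blinded review.

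It would be tempting to conclude that the primary result is compromised. The documents do not bear that out. The primary analysis uses the FAS by randomised arm, and a subject already counted as a CSRI stays counted whatever happens to dosing afterwards. What remains is later exposure in subjects treated with a listed agent before any CSRI, which should matter little. A reader might likewise suspect the denominators of the rate endpoints, since SAP 9.4.2 uses an offset for treatment exposure and SAP 10.1 removes interruptions from duration of exposure. The SAP does not say that the offset uses the 10.1 definition, so this is not established.

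**What to change.** Reconcile Sections 3.1 and 6.7.2 with Section 5.4.5 and Table 5-2, and have both permission sentences point to the governing list. Reconcile the ciprofloxacin, ritonavir and grapefruit juice entries in Appendix 1 with Table 5-2 and Section 6.3, so that each agent carries one instruction wherever it appears. Which instruction is right is for the sponsor's clinical team, and this review takes no position on it.

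The cost is a wording amendment or a clarification letter to sites. No analysis, sample size or data collection changes.

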3.2. Study Design Rationale

The study is designed as a standard randomized, double-blinded, placebo-controlled study to obtain efficacy and safety data for RTB101 in an unbiased fashion. Subjects will be prompted to fill out a Respiratory Illness Symptoms questionnaire in the eDiary daily in order to rapidly and accurately capture the occurrence of symptoms consistent with an RTI and to enable collection of nasopharyngeal swabs if they are able to within 48 hours of symptom confirmation when viral detection rates are highest ([Ginocchio et al., 2011](#)). Sixteen weeks of treatment is considered a sufficient duration to achieve a clinically meaningful reduction in clinically symptomatic respiratory illness during winter cold and flu season when there is a peak in the circulation of multiple respiratory viruses. PK samples will be obtained in approximately 400 subjects (200 in

each treatment group) at weeks 4 (or 6), 8, and 12 to enable characterization of PK after the study drug has reached steady state levels.

Study Population

Prevention of clinically symptomatic respiratory illness is particularly important in people age 65 and older in whom RTIs are a leading cause of hospitalization. Data from the Phase 2b trial RTB-BEZ235-202 suggests that RTB101 10 mg given once daily for 16 weeks during winter cold and flu season was safe and reduced the incidence of laboratory-confirmed RTIs in people age ≥ 65 . In addition, data from the RTB-BEZ235-202 study suggests that RTB101 had no benefit in elderly subjects who were current smokers or had a medical history of COPD. Therefore, the Phase 3 study will enroll subjects who are age ≥ 65 and who are not current smokers and do not have COPD. A Mini Mental Status Exam will be done at screening to ensure that subjects enrolled in the trial have the cognitive ability to understand the informed consent.

An effort will be made by monitoring screening to have at least 35% of the total subjects enrolled in the trial be from subgroups at increased risk of RTI-related morbidity and mortality (defined as age ≥ 85 or age ≥ 65 and <85 years with a medical history of asthma or congestive heart failure). Enhancing immune function and reducing the incidence of clinically symptomatic respiratory illness is of particular clinical relevance in these subgroups. RTIs are the second leading cause of hospitalization in people age ≥ 85 (Pfunter et al., 2013), the most common cause of asthma exacerbations (Nicholson et al., 1993), and the underlying cause of 16% of hospital admissions in patients with congestive heart failure (Chin and Goldman, 1997). Enrolling 35% of subjects from these subgroups is representative of the target ≥ 65 year old population since $\sim 10\%$ of those ≥ 65 have asthma (Gillman et al., 2012), 12% are ≥ 85 (U.S. Census 2010) and $\sim 10\%$ of individuals > 60 have congestive heart failure (Komanduri S et al., 2017).

Primary Endpoint

The primary endpoint of the study is the percentage of subjects who experience at least one clinically symptomatic respiratory illness beginning at least 3 days after the start of study drug treatment through Week 16. Clinically symptomatic respiratory illness is defined as respiratory illness symptoms that are consistent with a RTI based on prespecified diagnostic criteria and includes multiple types of RTIs (such as common cold, bronchitis, influenza-like illness, and pneumonia) caused by multiple different pathogens. Decreasing the incidence of clinically symptomatic respiratory illnesses is medically important in the elderly. Even respiratory illnesses such as upper RTIs that are normally mild in younger adults cause significant morbidity in the elderly (Nicholson et al., 1997) and significantly increase the risk of cardiovascular events (Musher et al., 2019). The incidence of all clinically symptomatic respiratory illness (with or without an associated laboratory-confirmed pathogen) was chosen as the primary endpoint

because some infectious pathogens may not be detected with the proposed laboratory detection methods. Data from Phase 2 studies suggest that RTB101 upregulates antiviral defenses and decreases the incidence of respiratory illness associated with multiple different viruses. Clinically symptomatic respiratory illnesses beginning at least 3 days after the start of study drug treatment will be analyzed because RTIs may have a 3-day incubation period. Therefore, RTIs occurring during the first 3 days of the study may have been acquired prior to initiation of study drug treatment. The clinical criteria that will be used in the Phase 3 trial to diagnose clinically symptomatic respiratory illnesses (see Section 6.7.1) capture RTI events that were also captured in the Phase 2b (RTB-BEZ235-202) trial. Prespecified clinical criteria will be used to diagnose clinically symptomatic respiratory illnesses to make sure that diagnosis is consistent across sites.

Secondary Endpoints

Secondary endpoints will include the incidence of clinically symptomatic respiratory illnesses associated with laboratory-confirmed pathogen(s). Assessment of clinically symptomatic respiratory illness that is associated with an infectious pathogen will allow assessment of the treatment effect of RTB101 on respiratory illness that is confirmed to be infectious in etiology. The incidence of clinically symptomatic respiratory illnesses associated with specific viruses (e.g., coronaviruses, hMPV, HRV/enterovirus, adenovirus, influenza A and B virus, parainfluenza viruses, and RSV) will also be assessed as a secondary endpoint to determine if RTB101 has consistent benefit across different viral infections, and to demonstrate no enhancement of any viral infection. Another secondary endpoint will be rate of clinically symptomatic respiratory illness because subjects may experience more than one respiratory illness during the 16-week treatment period, and RTB101 may decrease not just the percentage of subjects with clinically symptomatic respiratory illness but also the rate of clinically symptomatic respiratory illnesses. Additional secondary endpoints will determine if RTB101 decreases not only the incidence but also the severity and duration of respiratory illness symptoms. Decreasing the severity and duration of respiratory illness symptoms is a clinically important endpoint and will provide further evidence of the clinical benefit of RTB101.

Exploratory Endpoints

An exploratory endpoint will be the rate of viral respiratory infection, irrespective of whether the infection is symptomatic, to better assess the antiviral effects of RTB101. As an additional exploratory endpoint, healthcare resource utilization will be assessed because an important benefit of decreasing the incidence of clinically symptomatic respiratory illness may be a decrease in healthcare resource utilization by elderly subjects. Since decreasing the incidence of clinically symptomatic respiratory illness may improve the quality of life of elderly subjects, an

additional exploratory endpoint will be health related quality of life in all subjects assessed with the EQ-5D-5L questionnaire. The incidence of clinically symptomatic respiratory illness in subjects with a medical history of asthma or who are ≥ 85 years of age will be assessed as exploratory endpoints because these subpopulations had the greatest reduction on the incidence of laboratory confirmed RTIs after treatment with 10 mg RTB101 once daily as compared with placebo in the previous Phase 2b (RTB-BEZ235-202) trial. The incidence of asthma exacerbations in subjects with a medical history of asthma will also be assessed since RTIs are common causes of asthma exacerbations. Another exploratory endpoint will be the incidence of clinically symptomatic respiratory illness and the incidence of symptomatic respiratory illness associated with laboratory-confirmed pathogen(s) through Week 20 to assess if the efficacy of RTB101 persists for 4 weeks after subjects discontinue study drug. To better understand if the incidence of other types of infections may be reduced, the incidence of UTIs will be assessed. Finally, RNA expression and soluble serum biomarkers and pharmacogenomics (also known as pharmacogenetics) (Note: pharmacogenomics will only be assessed in those subjects who sign a separate consent form to allow collection of a pharmacogenomic (also known as pharmacogenetic) sample) will be assessed as exploratory endpoints to assess the effects of RTB101 on relevant immunologic markers and to potentially assess the impact of mTOR pathway polymorphisms in a pharmacogenomic analysis.

